	Mayo full clinical score	X			X			X		
	Mayo partial clinical score		X ^q	X			X			
	Patient diary to support mayo clinical score	X	X	X	X		X	X		
	Colonic biopsy	X			X			X		

Key: ALC = absolute lymphocyte count; ET = Early Termination; IP = Induction Period; MP = Maintenance Period; OCT = optical coherence tomography; OLP = Open-Label Period; PD = pharmacodynamic; PK = pharmacokinetic; TB = tuberculosis; WOCBP = women of child-bearing potential.

Footnotes to Table 1

- a. The duration of Visit 1 will be approximately 7 hours. Prior to dosing a 12-lead ECG will be performed and following dosing patients will have hourly vital signs recorded at 1, 2, 3, 4, 5 and 6 hours (± 10 minutes) postdose. A further 12-lead ECG will be performed at the end of the observation period.
- b. Study visits should be scheduled in the morning, where possible, and on study visit days patients should be instructed to withhold the dose until the study visit and the dose should be administered during the visit.
- c. Just prior to dosing at Visit 1, patients will begin 24-hours of Holter monitoring. Patients will not be expected to remain on site for the 24-hour duration as monitoring will continue at home.
- d. IP Week 4 and IP Week 8 occur 4 and 8 weeks, respectively, following the completion of dose escalation, ensuring 8 weeks of dosing at the assigned dose.
- e. Medical history will include smoking history. The Day 1 medical history can be abbreviated, noting events that occurred between Screening and Day 1.
- f. Screening for TB will include a review of past history, current physical exam. A chest X-ray will be obtained for those subjects who do not have a chest X-ray within 6 months prior to screening and either a tuberculin skin test or a QuantiFERON[®] gold test for TB.
- g. Serology testing will be performed at screening to determine the patient's immune status with respect to the following viruses: varicella zoster virus (VZV), human immunodeficiency virus (HIV) antibodies, hepatitis B surface antigen (HBsAg) and anti-hepatitis B core antigen (HBcAg) IgM, anti-hepatitis C virus (HCV) IgG or IgM, should be assessed at screening in all patients.
- h. At screening the stool sample should be used to rule out serious infection and should include evaluation for *C. difficile* toxin as well as ova and parasitic examination.

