13.11. Missing Data

For the primary analysis, as well as for the analyses of all key secondary efficacy endpoints that are defined as proportions, patients who do not provide data at the specified time point will be classified as nonresponders.

The Mayo score used for clinical endpoints in the study will utilize the Mayo endoscopy score derived from the central reader. In the case that a central endoscopic result is missing and the endoscopic subscore read by the Investigator will be utilized.

One of the key secondary efficacy endpoints (change in Mayo score) is a quantitative endpoint. For the key secondary analyses of this variable, missing values will be replaced by the least favorable observed change observed in the placebo group.

Sensitivity analyses of the primary and key secondary endpoints will be carried out to investigate the impact of missing data on the efficacy conclusions. These will include analyses of completed cases, observed cases, and multiple imputation model-based methods.

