5.2.2. Mayo Score

The Mayo score is a standardized, accepted, numerical scale used to evaluate disease severity in people with UC.

The Mayo score consists of four subscores, each ranging from (0-3) for a total score that ranges from 0 to 12:

- 1. Stool frequency^a
 - 0=Normal number of stools for this patient
 - 1 = 1 to 2 stools more than normal
 - 2=3 to 4 stools more than normal
 - 3=5 or more stools more than normal
- 2. Rectal bleeding^b
 - 0=No blood seen
 - 1 = Streaks of blood with stool less than half the time
 - 2=Obvious blood with stool most of the time
 - 3 = Blood alone passes
- 3. Findings on endoscopy
 - 0=Normal or inactive disease
 - 1 = Mild disease (erythema, decreased vascular pattern, mild friability)
 - 2 = Moderate disease (marked erythema, lack of vascular pattern, friability, erosions)
 - 3 = Severe disease (spontaneous bleeding, ulceration)
- 4. Physician's global assessment^c
 - 0 = Normal
 - 1 = Mild disease
 - 2 = Moderate disease
 - 3 = Severe disease

- ^a Each patient serves as his or her own control to establish the degree of abnormality of the stool frequency.
- ^b The daily bleeding score represents the most severe bleeding of the day.
- ^c The physician's global assessment acknowledges the three other criteria, the patient's daily recollection of abdominal discomfort and general sense of well-being, and other observations, such as physical findings and the patient's performance status.

The Mayo score will be derived at all visits when an endoscopy is performed. For these visits, the Mayo score will be derived using the endoscopy subscore and the non-endoscopy subscores performed at the same nominal visits, even if the assessments have different dates. The baseline Mayo score will be derived from the most recent endoscopy subscore (Item 3) completed during Screening and the last non-missing non-endoscopy subscores (i.e., Items 1, 2, and 4) prior to initial study drug administration.

Partial Mayo scores are calculated using data from Items 1, 2, and 4 only.

Mayo scores are calculated using:

- 1. The stool frequency and rectal bleeding data form the most recent consecutive 3-day period prior to the visit, excluding the following:
 - a. The day medications for constipation, diarrhea, or bowel irregularity are taken
 - b. The day(s) of a procedure or preparation for a procedure (e.g., enemas, other laxative, clear liquid diet) that would affect bowel frequency or blood content of the stool

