6.4. Missing values

The Mayo score used for clinical endpoints in the study will utilize the Mayo endoscopy score derived from the central reader. In the case that a central endoscopic result is missing the endoscopic subscore read by the Investigator will be utilized.

For calculation of the Mayo score for the efficacy endpoints, at least 2 of the 4 subscores must be available to calculate the total Mayo score. A missing subscore(s) will be carried forward from the most recent previous visit for which the subscore is available. The endoscopy subscore is not considered missing if the Investigator endoscopic subscore is available. If more than 2 subscores are missing, then the Mayo score will be considered missing.

For calculation of the partial Mayo score for the efficacy endpoints, at least 2 of the 3 subscores must be available to calculate the partial Mayo score. The missing subscore will be carried forward from the previous visit. If more than 1 subscore is missing, then the partial Mayo score will be considered missing.

For the primary analysis, as well as for the analyses of all key secondary efficacy endpoints that are defined as proportions, patients who have missing Mayo or partial Mayo scores at the specified time point will be classified as nonresponders.

One of the key secondary efficacy endpoints (change in Mayo score) is a quantitative endpoint. For the key secondary analysis of this variable, missing values will be replaced by the last observation carried forward (LOCF). If no post-Baseline observation is available to carry forward, then the average score for the observed values within the same treatment group will be used, rounded to the nearest integer.

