6.16. Dosing Compliance

6.17. Treatment Compliance

6.18. Prior and Concomitant Medications

6.19. Efficacy Analyses

Analysis of all efficacy endpoints will primarily be based on the ITT population with treatment failure rules applied. Patients will be considered to have failed treatment if they have protocol-prohibited changes in concomitant UC medications, including an increase in corticosteroid dose from baseline to treat UC or a prolonged course of systemic corticosteroids >7 days for treatment of disease other than UC; initiation of an immune suppressing therapy including 6-MP or azathioprine or anti-TNF agents; a colectomy (partial or total) or an ostomy; or have discontinued study agent for lack of therapeutic effect before the week 8 evaluations. Patients with a treatment failure will be considered not to have achieved the dichotomous end points; and for continuous end points, their last values will be carried forward for all

visits subsequent to the time of treatment failure. Treatment failure rules will supersede other data handling rules.

The efficacy endpoints will also be analyzed in the PP population.

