6.19.3. Secondary Efficacy Analyses

If the primary efficacy analysis is statistically significant (p < 0.05), then additional confirmatory tests using the ITT population will be performed in the following prespecified order:

- Proportion of patients in clinical response at Week 8: 1 mg dose versus placebo
- Proportion of patients in clinical response at Week 8: 0.5 mg dose versus placebo
- Change in Mayo score from baseline at Week 8: 1 mg dose versus placebo
- Change in Mayo score from baseline at Week 8: 0.5 mg dose versus placebo
- Proportion of patients with mucosal healing at Week 8: 1 mg dose versus placebo
- Proportion of patients with mucosal healing at Week 8: 0.5 mg dose versus placebo

Provided that all previously specified tests are statistically significant (p < 0.05), each of these comparisons will be assessed using a two-sided test at the 0.05 level of significance. However, if a comparison is not statistically significant, then all subsequent comparisons will be considered exploratory.

Secondary endpoints that are defined as proportions will be analyzed using the same type of methodology as described for the primary analysis. Analyses of all proportion endpoints using the CMH test will be completed using the data from the two groups being compared. Quantitative secondary endpoints such as change in Mayo score will be analyzed using analysis of covariance (ANCOVA) models with effects for treatment group and prior anti-TNF therapy experience, and with the baseline value of the corresponding endpoint included as a covariate. All secondary analyses will be carried out using two-sided test at the 5% level of significance.

Actual and change from baseline in Mayo scores over time will be plotted.

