8. DEVIATIONS FROM PROTOCOL

The analyses of the following endpoints specified in the protocol are not performed due to collected samples have not been analyzed at the time of database lock.

- Proportion of patients with histologic Remission at Week 8 for exploratory objectives and exploratory efficacy endpoints.
- Plasma protein biomarkers (cytokines, chemokines, other inflammatory proteins) as PD endpoint.

STATISTICAL ANALYSIS PLAN - OPEN LABEL PERIOD ADDENDUM

Title: A Phase 2, multi-center, randomized, double-blind, placebo-

controlled parallel-group study to evaluate the clinical efficacy and

safety of induction therapy with RPC1063 in patients with

moderately to severely active ulcerative colitis

Protocol: RPC01-202

Sponsor: Celgene International II Sàrl (see appended signature page)

[name] [name]

[contact]

Date: October 15, 2019

Status: Addendum to Version 2.0

CONFIDENTIAL

This document is a confidential communication of Receptos. Acceptance of this document constitutes agreement by the recipient that no unpublished information contained herein shall be published or disclosed without prior written approval, except that this document may be disclosed to the appropriate Institutional Review Board(s)/Independent Ethics

Committee(s) under the condition that they keep it confidential.

TABLE OF CONTENTS

SIGNA	ATURES	2
TABLE	E OF CONTENTS	3
LIST O	OF ABBREVIATIONS	4
1.	Introduction	5
2.	Study Design	5
3.	Analysis Cohorts	5
4.	DMC	5
5.	Patient Disposition	5
6.	OLP Baseline	5
7.	Efficacy Analyses	6
7.1.	Endpoints	6
7.2.	Mayo Score at the End of OLP	6
7.3.	Visit Windows	7
8.	Safety Analyses	8
9.	Guideline on Missing Date Imputation	8

LIST OF ABBREVIATIONS

AE adverse event DEF definition

DMC data monitoring committee

IP Induction Period ITT intent-to-treat

[figure not shown]
MP Maintenance Period

NRI Non-responder imputation
OLP Open-Label Treatment Period

SAE serious adverse event SAP statistical analysis plan

UC ulcerative colitis

1. Introduction

Study Design

3. Analysis Cohorts

- Intent-to-Treat (ITT) Analysis Cohorts will be labeled by randomized treatment in the parent study for all subjects who received at least one dose of RPC1063 1mg in OLP.
- Safety Analysis Cohorts will be labeled by actually received treatment in the parent study for all subjects who received east one dose of RPC1063 1mg in OLP.

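### Missing Week 8 Mayo change: SAP 6.4 departs from protocol 13.11 without listing it, and its own-arm-average fallback makes the standard error too small

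*SAP*

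**What the plan says.** Protocol 13.11 has one rule for the quantitative key secondary endpoint, change in Mayo score: "missing values will be replaced by the least favorable observed change observed in the placebo group".

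SAP 6.4 has a different rule in two steps. The last observation is carried forward. "If no post-Baseline observation is available to carry forward, then the average score for the observed values within the same treatment group" is used, rounded to an integer.

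SAP Section 8 is the place for departures from the protocol. It opens "The analyses of the following endpoints specified in the protocol are not performed due to collected samples" and lists only Week 8 histologic remission and the plasma protein biomarkers. It does not mention imputation.

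Other provisions decide who is affected:

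- SAP 5.2.2: "The Mayo score will be derived at all visits when an endoscopy is performed". In protocol Table 1 the row "Mayo full clinical score" is marked at screening, Week 8 and Week 32/early termination. Week 4 has the partial score only.
- SAP 6.4 calculates a total when at least two of the four subscores are available. For proportions, "patients who have missing Mayo or partial Mayo scores at the specified time point will be classified as nonresponders".
- SAP 6.19 carries the last value forward for treatment failures, and "Treatment failure rules will supersede other data handling rules".
- SAP 6.19.3 tests in fixed order: "if a comparison is not statistically significant, then all subsequent comparisons will be considered exploratory".
- SAP 6.19.5 plans observed-case and multiple-imputation sensitivity analyses.

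**The concern.** There are three separate problems.

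1. **The documents disagree.** Protocol 13.3 leaves the SAP to fill in detail, but here it replaces the rule, and Section 8 does not say so.
2. **The fallback adds patients without information.** A patient given the arm average adds almost nothing to the residual variation, yet counts in the sample size and degrees of freedom. The standard error and p-value are then too small. SAP 6.19.3 names no confidence interval for this ANCOVA, but any interval taken from it would be too narrow.
3. **The wording allows two programs.** 'Average score' can mean the arm's mean Week 8 score less the patient's own baseline, or the arm's mean change. With arm means of 9 at baseline and 6 at Week 8, a patient with baseline 12 gets 6 - 12 = -6 on the first reading and 6 - 9 = -3 on the second.

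The same patient is also treated in opposite ways: a nonresponder for the proportion endpoints, but an average performer on Mayo change.

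**Working it through.** **Inputs.** From the documents: about 60 patients per arm (SAP 6.5); ANCOVA with treatment, prior anti-TNF experience and baseline, two-sided 5%, in fixed order (SAP 6.19.3). Neither document gives an SD, standard error, power or dropout rate for this endpoint, so there is no stated figure to reproduce. The one power statement (10% against 31%) concerns remission and is not used here. Assumed: 1 to 6 of 60 patients per arm reaching the fallback; residual SD 3; integer baseline about 8.5 (SD 1.5, range 6 to 12); scores limited to 0 to 12.

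**Who reaches the fallback.** A dosed patient who is not a treatment failure, has more than two Week 8 subscores missing, and has no early-termination full Mayo. No full Mayo is scheduled between screening and Week 8, so for such a patient there is nothing to carry forward.

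**Closed form.** Let a share m of n patients per arm be filled with the arm mean.

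- Residual variation comes only from the n(1-m) observed patients but is divided by about n, so the variance estimate is about (1-m)σ².
- Reported variance of the difference: about 2(1-m)σ²/n.
- Actual variance: about 2σ²/[n(1-m)].
- The ratio is (1-m)², so the reported standard error is (1-m) times the actual one.
- Type I error = 2[1 - Φ(1.96(1-m))].

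**Simulation.** 20,000 null trials per row, three-arm ANCOVA, dropout at random, both readings of the rule.

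| Imputed per arm | 1-m | Closed-form type I error | Simulated (score / change reading) | Reported SE / actual SD |
|---|---|---|---|---|
| 1 of 60 | 0.983 | 5.4% | 5.4% / 5.5% | 0.98 |
| 2 of 60 | 0.967 | 5.8% | 6.0% / 6.1% | 0.96 |
| 3 of 60 | 0.950 | 6.3% | 6.2% / 6.3% | 0.95 |
| 6 of 60 | 0.900 | 7.8% | 7.9% / 7.7% | 0.88-0.90 |

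Another simulation, with Week 8 SD 3.0 and a baseline to Week 8 correlation of 0.3 or 0.75, gave 6.1-6.6% at 5% missing and 6.9-8.4% at 10%.

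**Alternatives under the null.** Observed cases: 5.0-5.2%. Multiple imputation on arm, anti-TNF experience and baseline: 5.3%, 5.1% and 5.2% with 2, 3 and 6 per arm. With Week 4 partial Mayo added, run at 3 and 6 per arm: 5.0-5.3%, with an SE ratio of about 1.0.

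**Effect through the gates.** Placebo and 0.5 mg change -2, 1 mg change -4. The gates are 1 mg remission, 1 mg response and 0.5 mg response, simplified by leaving out the rectal-bleeding and subscore conditions. False 0.5 mg Mayo-change claims are 1.0% with none imputed, and 1.3%, 1.1%, 1.2% and 1.1% with 1, 2, 3 and 6 per arm. A run of 48,000 trials per row (score reading) gives 1.13%, 1.16%, 1.20%, 1.19% and 1.16%, which is flat.

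**Possible bias.** True changes are placebo -2.0 and active -3.5, and the imputed patients do not improve. 'Actual' is the same ANCOVA with the dropouts' real values.

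| Missing, placebo / each active arm | Actual | SAP rule | Multiple imputation | Protocol rule |
|---|---|---|---|---|
| 1/60 and 5/60 | -1.19 | -1.42 | -1.42 | -0.89 |
| 1/60 and 3/60 | -1.29 | -1.42 | -1.42 | -1.14 |

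The SAP rule overstates the effect by 1.42 - 1.19 = 0.23 and 1.42 - 1.29 = 0.13. The protocol rule understates it by 1.19 - 0.89 = 0.30 and 1.29 - 1.14 = 0.15. If the imputed patients resemble completers, the SAP rule has no shift (-1.43 against -1.43).

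**The case against.** The strongest reply is that nothing confirmatory changes. Mayo change is tested only after remission and response succeed, and those gates count missing patients as failures, so the false-claim rate stays near 1%. **This stands**, and it is why the point is minor.

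The affected group is also narrow, since sites must try to obtain the early-termination assessments, and nothing in the documents supports 6 of 60. **This stands too.** At 1 or 2 per arm the standard error is only 2-4% low, and if nobody reaches the fallback only the textual conflict and the ambiguity remain.

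The SAP may have been written against another protocol version: its section 5.3 collects adverse events to 30 days, while protocol 12.1 uses 90. That version is not available, so an omission from Section 8 when it was written cannot be shown. **What stands** is that the two current texts differ and the difference is unlisted.

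The planned sensitivity analyses would expose the distortion. They would, but the headline test would still use the flawed value. The two readings also behave almost alike at trial level, although they give individual patients different values.

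Finally, the protocol rule could simply be restored. With equal dropout it is conservative: type I error is about 3%, 1.7% and 1.0% at 5%, 10% and 20% missing. With unequal dropout it can fail the other way: 14.3% under the null with 9/60 missing on placebo and 3/60 per active arm, and 5.5% with 3/60 and 1/60. The first of these lies outside the 1-6 range used above. Neither single-value fill gives a correct standard error.

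**Conclusion.** The concern holds, at minor severity. The rules differ, Section 8 is silent, and the own-arm average shrinks the standard error by a factor of about (1-m) on either reading whenever it is used. The direction is certain. The size depends on a count the documents do not give: an SE about 2% low with 1 patient per arm, and 10-12% low with 6. The simulations rest on assumed effects, SD and missing counts.

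The damage is to the reported precision and p-value of one key secondary endpoint, not to the rate of false confirmatory claims. Bias is not the reason to change, because multiple imputation shows the same lean if the imputed patients did worse than completers.

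**What to change.** - In SAP 6.4, delete the own-arm-average sentence. This also removes the ambiguity.
- For patients outside the 6.19 treatment-failure rule who have no post-baseline full Mayo, make the multiple imputation planned in 6.19.5 the main method. Use arm, prior anti-TNF experience, baseline Mayo and Week 4 partial Mayo, combined by Rubin's rules.
- Keep observed cases and the protocol 13.11 rule as sensitivity analyses, noting that the protocol rule is not neutral when dropout is unequal.
- Report the number imputed per arm.
- List the difference from protocol 13.11 in SAP Section 8.

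The cost is SAP wording and minor programming, since the method is already planned. The interval widens to its proper width. Mean SE is 0.535 instead of 0.517 with 2 patients per arm (ratio 1.03), 0.539 instead of 0.513 with 3 (1.05), and 0.556 instead of 0.500 with 6 (1.11).

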6.5. Sample Size

Approximately 300 patients will be screened to ensure that 180 patients are randomized in the IP, assuming a 40% screen failure rate. Patients will be enrolled in a 1:1:1 randomization with approximately 60 patients assigned per treatment arm.

The sample size is justified with respect to the comparison of remission rates at the end of the IP between an RPC1063 group and the placebo group. Based on the use of a two-sided test at the alpha=0.05 level of

significance, and assuming a placebo remission rate of 10%, a sample size of 60 patients per group will provide 80% power to detect an improvement in the remission rate of 21 percentage points or larger (i.e., an active group remission rate of 31% or larger).

6.6. Study Blinding, Patient Identification and Replacement of Patients

Investigational medicinal product and placebo capsules will be identical in physical appearance. The treatment each patient will receive will not be disclosed to the Investigator, study center personnel, patient, Sponsor and their representatives. The treatment codes will be held according to an Interactive Voice Response System (IVRS). Further instructions will be provided in a separate IVRS manual.

Patients will be assigned a unique patient number and will only be identified by their patient number and their initials on all study documentation.

Patients who discontinue from the study following randomization will not be replaced.

6.7. Enrollment and Randomization Procedures

A patient is considered enrolled in the study when the informed consent form is signed at the screening visit.

Patients will be randomized into the study on Day 1 using the IVRS system.

Patients will be randomized 1:1:1 to receive placebo, RPC1063 0.5 mg, or RPC1063 1 mg. The randomization will be stratified by prior anti-TNF therapy (yes vs. no).

